18.4. Informed Consent

Informed Consent for each patient will be obtained prior to initiating any trial procedures in accordance with the "IBCSG Patient Information Sheet and Informed Consent" (See Appendix I). One signed and dated copy of the Informed Consent must be given to each patient and the original copy must be retained in the Investigator's trial records. The Informed Consent Form must be available in the case of data audits. Verification of signed Informed Consent and the date signed are required for randomization to this trial.

The "Declaration of Helsinki" recommends that consent be obtained from each potential patient in biomedical research trials after the aims, methods, anticipated benefits, and potential hazards of the trial, and discomfort it may entail, are explained to the individual by

the physician (<http://www.wma.net/en/30publications/10policies/b3/index.html>). The potential patient should also be informed of her right to not participate or to withdraw from the trial at any time. The patient should be told that material from her tumor will be stored and potentially used for additional studies not described in this protocol.

If the patient is in a dependent relationship to the physician or gives consent under duress, the Informed Consent should be obtained by an independent physician. If the patient is legally incompetent (i.e., a minor, or mentally incompetent), Informed Consent must be obtained from the parent, legal guardian, or legal representative in accordance with the law of the country in which the trial is to take place. By signing this protocol, the Investigator agrees to conduct the trial in accordance with Good Clinical Practice and the "Declaration of Helsinki."

The IBCSG recognizes that each institution has its own local, national, and international guidelines to follow with regard to Informed Consent. Therefore, we provide a template information sheet and Informed Consent Form (Appendix I), which can be downloaded and edited to incorporate information specific to your institution (see www.ibcsg.org). The template Patient Information Sheet and Informed Consent has been written according to ICH guidelines which state the Informed Consent should adhere to GCP and to the ethical principles that have origin in the "Declaration of Helsinki". The final version should receive the Institutional Review Board/ Local Ethics Committee approval in advance of its use. Centers should send their locally modified PIS/IC to the IBCSG Data Management Center for review and approval before submitting to their Ethics Committee.

18.5. Premature withdrawal

18.5.1. Withdrawal from trial treatment

Patients have the right to refuse further trial treatment at any time during the trial. Patients may also be withdrawn at any time from trial treatment at the discretion of the Investigator due to an adverse event, or based on any other relevant medical condition. Such patients will remain in the trial and will proceed to surgery. The patient will continue to be documented according to protocol.

18.5.2. Change of consent

Patients have the right to withdraw consent for further trial participation at any time without having to specify the reason. The data recorded up to the time point of withdrawal will continue to be evaluated in the trial. The Investigator should ask the patient for her consent to continue to be documented according to protocol.

It should be documented in both the medical records and in the eCRF (Form 41-COC) whether it is acceptable for the patient to be documented according to protocol despite her withdrawal of study consent.

19. Governance and Administrative Considerations

19.1. Insurance

IBCSG will contract the appropriate liability insurance for this trial. Patients who suffer injuries due to the trial should report them immediately to their physician. The local Center should report all alleged claims immediately to the IBCSG.

19.2. Steering Committee

A Steering Committee will be constituted for this trial. The primary responsibilities of the Steering Committee are twofold. First, the Steering Committee is responsible for maintaining the scientific integrity of the trial, for example, by recommending changes to the protocol in light of emerging clinical or scientific data from other trials. Second, the Steering Committee is responsible for the translation of recommendations of the IBCSG Data and Safety Monitoring Committee into decisions. Membership will include IBCSG officials, study chair and co-chairs, trial statisticians, representatives from some Participating Centers, and representatives from Ferring Pharmaceuticals.

General partition of responsibilities:

The Steering Committee has the authority to make and implement any final decisions, such as substudies of the trial or amendments to the trial protocol, and may recommend the termination/early termination of the trial.

The IBCSG Executive Committee is responsible for the implementation of all final decisions taken by the Steering Committee.

The IBCSG Foundation Council decides on the termination/early termination of the trial.

19.3. Data and Safety Monitoring Committee (DSMC)

The trial will be presented for review to the IBCSG Data and Safety Monitoring Committee (DSMC) at each of their semi-annual meetings. Accrual and safety will be monitored.

19.4. Premature discontinuation of the trial

The trial may be discontinued early in parts or completely if the information on the trial treatment leads to doubt as to the benefit/risk ratio.

19.5. Quality Assurance

The IBCSG conducts trials according to the ICH Good Clinical Practice (GCP) guidelines. The Trial IBCSG Data Manager reviews each eCRF. In addition, the IBCSG Medical Reviewer reviews each case at specific timepoints. The IBCSG conducts periodic audit visits to ensure proper trial conduct, verify compliance with GCP, and perform source data verification.

The Investigator should ensure that source documents are made available to appropriately qualified personnel from IBCSG or its designees, or to health authority inspectors after appropriate notification.

Ferring-designated staff and quality assurance auditors may audit the conduct of any site and shall be granted reasonable access to facilities during normal business hours. Such auditors shall not be entitled to access, make copies of the source documents and/or to take them away.

At regular intervals during the clinical trial, the Center will be contacted, through monitoring visits, letters or telephone calls, by a representative of the Monitoring Team to review study progress, Investigator and patient compliance with clinical trial protocol requirements and any emergent problems. These monitoring visits will include but not be limited to review of the following aspects: patient Informed Consent, patient recruitment and follow-up, SAE documentation and reporting, AEs with pre-specified monitoring documentation and reporting, AE documentation, trial treatment administration, patient

compliance with the regimens, drug accountability, concomitant therapy use and quality of data.

19.6. Data protection

A unique Patient Identification Number (ID) will be assigned by the IBCSG Registration/Randomization System to each patient randomized into the trial. The names of the patients will not be disclosed to the IBCSG.

Only the Patient ID will be used to identify a patient on the eCRF. Identification of patients must be guaranteed at the Participating Center. In order to avoid identification errors, Centers should keep a Patient Identification Log containing the patients' name, year of birth, hospital number and the Patient ID allocated by IBCSG.

Regulatory authorities and the pertinent Ethics Committee (ERB/IRB) may have access to patient data on-site. IBCSG audit or monitoring personnel will also have access to such data on-site.

| NCI CTCAE | National Cancer Institute common toxicity criteria for adverse events |
| DMC | Data Management Center (IBCSG) |
| DSMC | Data and Safety Monitoring Committee |
| ECOG PS | Eastern Cooperative Oncology Group Performance Status |
| E2 | 17- β -estradiol |
| eCRF | Electronic case report form |
| ER | Estrogen receptor |
| FFPE | Formalin fixed paraffin embedded |
| FSH | follicle-stimulating hormone |
| FSTRF | Frontier Science and Technology Research Foundation |
| GCP | Good clinical practice |
| GnRH | Gonadotropin-releasing hormone |
| H&E | Hematoxylin and eosin |
| HER2 | Human epidermal growth factor 2 |
| HR | Hazard ratio |
| i.m. | intramuscular |
| IBCSG | International Breast Cancer Study Group |
| IC | Informed Consent |
| ICH | International conference on harmonization |
| iDF | iDataFax |
| INN | International Non-proprietary Name |
| IUN | Intra-Uterine Device |
| LH | luteinizing hormone |

| | |
|------|---|
| LHRH | luteinizing hormone-releasing hormone |
| OS | Overall survival |
| PFS | Progression-free survival |
| PgR | Progesterone receptor |
| PD | Progressive disease |
| PEPI | Preoperative Endocrine Prognostic Index |
| PR | Partial response |
| PRS | Patient-reported symptoms |
| s.c. | subcutaneous |
| SAE | Serious adverse event |
| SD | Stable disease |
| SERM | selective estrogen receptor modulator |
| SPC | Summary of product characteristics |
| ULN | Upper limit of normal |
| USAN | United States Adopted Name |
| WHO | World Health Organization |

1 STUDY OVERVIEW

1.1 SYNOPSIS

The TREND randomized phase II trial evaluates neoadjuvant endocrine therapy (degarelix [GnRH antagonist] versus triptorelin [GnRH agonist]) in combination with letrozole as treatment for premenopausal women diagnosed with endocrine-responsive cancer. A 1:1 randomization allocation (degarelix+ letrozole vs triptorelin +letrozole) is used. The primary objective is to compare the endocrine activity of neoadjuvant degarelix and triptorelin in premenopausal patients receiving letrozole for primary endocrine-responsive breast cancer. The endocrine activity is measured by time to optimal ovarian function suppression, with the hypothesis that degarelix will achieve faster ovarian suppression than triptorelin.

The study was activated on 28 March 2013 and the first patient was enrolled on 24 February 2014, with the delay due to changes in trial activation rules in Italy during that time.

[figure not shown]
The trial activated in seven participating centers in Italy: Bologna, Genoa, Milan, Pavia, Prato, Rimini, and Varese.

1.2 TRIAL DESIGN

TREND (TRIAL 41-13) OVERVIEW

Title	Trial on the Endocrine activity of Neoadjuvant Degarelix (TREND): A randomized phase II trial evaluating the endocrine activity and efficacy of neoadjuvant degarelix versus triptorelin in premenopausal patients receiving letrozole for primary endocrine responsive breast cancer
Patient Population	Premenopausal patients with histologically confirmed primary breast cancer and with primary tumor which is ER+ and PgR+ (>50%) and HER2-negative or not amplified
Entry	Patients must be entered before initiating any treatment for primary invasive breast cancer. Patients cannot have received GnRH analogue, SERM or AI within 12 months prior to randomization, and cannot have used hormonal treatment in the two months prior to randomization. Premenopausal status must be determined by estradiol (E2) above 54 pg/mL (or above 198 pmol/L), measured in a local laboratory within 14 days prior to randomization.
Activation Date	28 March 2013 (first patient entered 24 February 2014)
Target Accrual	50
Closure Date	12 January 2017 (Last patient enrolled 10 January 2017)
Final Accrual	51

Schema:

Stratification Factors:

Age: ≤39 versus 40+ (years).

Treatment Schedules:

Arm A: Triptorelin 3.75 mg administered intramuscularly (i.m.) on day 1 of every cycle* + letrozole 2.5 mg/day orally for 6 cycles

Arm B: Degarelix 240 mg given as two subcutaneous injections (s.c.) of 120 mg on day 1 of cycle* 1, followed by 80 mg sc on day 1 of cycles 2 to 6 + letrozole 2.5 mg/day orally for 6 cycles

*one cycle is 28 days

Blood Sampling Schedule:

Blood will be sampled at the following times to determine estradiol (E2) levels in a central laboratory:

- Baseline: day 1 of the first treatment cycle before the administration of the first dose of degarelix or triptorelin
- 24 and 72 hours thereafter
- 7 days and 14 days after the first injection
- Day 1 of cycles 2 to 6 before the administration of degarelix or triptorelin.

1.3 STATISTICAL DESIGN AND SAMPLE SIZE

50 patients will be randomized using 1:1 allocation and stratified based on age (≤ 39 vs. ≥ 40 years). to

- 25 patients to treatment with triptorelin plus letozole; and
- 25 patients to treatment with degarelix plus letozole.

The sample size was determined in consideration of the trial primary objectives. Specifically, the primary endpoint of time to optimal ovarian function suppression will be assessed in the two treatment arms and is defined as time from the first injection of degarelix or triptorelin to the first centrally assessed E2 ≤ 2.72 pg/mL or ≤ 10 pmol/L during the 6 cycles of neoadjuvant treatment. The blood samples are taken at day 1 of the first treatment cycle before the administration of the first dose of degarelix or triptorelin (baseline), and thereafter at 24 and 72 hours, 7 days and 14 days after the first injection, and on day 1 of cycles 2 to 6 before the administration of degarelix or triptorelin.

The following table provides the assumption on the cumulative percent of patients who are anticipated to reach optimal ovarian function suppression (E2 level ≤ 2.72 pg/mL or ≤ 10 pmol/L) during the 6 cycles of neoadjuvant treatment.

Treatment arms	Cumulative percent (%) of patients with E2 ≤ 2.72 pg/mL or ≤ 10 pmol/L				
	2 weeks	4 weeks	8 weeks	12 weeks	16 weeks
Triptorelin+Letrozole (control: arm A)	30	60	75	90	100
Degarelix+Letrozole (experiment: arm B)	60	95	100	100	100

With 23 patients in each treatment arm and based on the assumption in the table above, the study has 90% power to detect a difference in time to optimal ovarian function suppression (E2 ≤ 2.72 pg/mL or ≤ 10 pmol/L) between the two treatment arms, using a two-sample log-rank test at a two-sided significance level of 0.05. Calculations were performed using nQuery Advisor® (logrank test of survival in two groups, simulation with percentages specified in above table).

To allow for missing data, the study enrolls 25 patients to each treatment arm for a total of 50 patients.

1.4 TRIAL CONDUCT

1.4.1 Protocol Versions/Amendments

The trial was activated with protocol version 1.0 on dated 28 March 2013, and first patient enrolled on 24 February 2014. Final patient enrolled in January 2017 with final enrollment of N=51.

There is no amendment.

1.4.2

IBCSG Data and Safety Monitoring Committee (DSMC) conducts regularly scheduled semi-annual reviews of interim clinical and safety data for trial 41-13 (TREND)

The DSMC conducted reviews on April 24, 2014 and subsequently around every 6 month, concluded the trial to continue as planned.

2 OVERVIEW OF ANALYSIS PLANS

Analysis Steps:

- Identify patients who are enrolled into two arms and check the treatment status.
- Define primary endpoint using data from the relevant CRFs and centrally assessed E2 values at timepoints.
- Define (baseline clinical) covariates for model adjustment and calculate age stratification factor (at randomization)
- Use the method described below for analyses.

2.1 ANALYSIS POPULATIONS

ITT population: All randomized patients without regard to adherence with treatment assigned.

The safety population: All patients who received at least one dose of trial treatment were included in assessments of safety and tolerability

Surgery population: All patients who received surgery at the end of neoadjuvant therapies.

PRS population: All patients who received at least one dose of trial treatment and had at least one FACT-ES assessment were included in the analysis.

2.2 ANALYSIS PLANS

2.2.1 Primary Objective

To compare the endocrine activity of neoadjuvant degarelix and triptorelin in premenopausal patients receiving letrozole. The endocrine activity is measured by time to optimal ovarian function suppression.

2.2.2 Secondary Objectives

To evaluate:

- Node-negative disease at surgery
- Breast-conserving surgery (BCS) rate
- The Preoperative Endocrine Prognostic Index (PEPI) score determined after completion of neoadjuvant therapy or at the time of surgery
- Ki67 proliferation marker changes
- Best overall (disease) response
- Safety and tolerability as documented according to NCI CTCAE version v4.0
- Patient-reported symptoms (PRS) outcomes

2.2.3 Primary Endpoint

Time to optimal ovarian function suppression (TTOFS): time from the first injection of degarelix or triptorelin to the first assessment of centrally assessed 17- β -estradiol (E2) level in the range of optimal ovarian function suppression ($E2 \leq 2.72$ pg/mL or ≤ 10 pmol/L) during the 6 cycles of neoadjuvant treatments. Time for patients who do not reach the targeted E2 level will be censored at the last E2 assessment date.

2.2.4 Secondary Endpoints

1. Node-negative disease at surgery: The number of lymph nodes assessed at surgery minus the number of positive nodes identified, equal to zero.
2. Breast-conserving surgery (BCS): Whether or not patient undergoes BCS (per Surgery form). If patient does not undergo surgery within the trial then patient is to be excluded from the surgery outcome summary (analysis is based on surgery population)
3. Change in Ki67 expression level: the percent change in Ki67 expression from pre-treatment diagnostic (baseline) biopsy to surgery, calculated as (surgery-baseline)/baseline*100.
4. The Preoperative Endocrine Prognostic Index (PEPI, range 0-12) score at time of surgery: By integrating central pathology review (CPR) results of pathological features and biomarkers with risk points (table below), the PEPI is the sum of the risk points with a 0 score representing the best prognostic feature, as previously determined to be associated with recurrence-free survival (RFS):

Pathology, biomarker status	RFS	
	HR	Adverse Points
Tumor size:		
T1/2		0
T3/4	2.8	3
Nodal status		
Negative		0
Positive	3.2	3
Ki67 level		
0 – 2.7% (0 – 1 ^a)		0
>2.7 – 7.3% (1 – 2 ^a)	1.3	1

>7.3 – 19.7%	(2 – 3 ^a)	1.7	1
>19.7 – 53.1%	(3 – 4 ^a)	2.2	2
>53.1%	(>4 ^a)	2.9	3
ER status, Allred score			
0 – 2		2.8	3
3 – 8			0

^aThe natural logarithm interval corresponding to the per cent Ki67 values on the original percentage scale

5. Best overall response: based on WHO tumor measurement and response criteria [1], measured from the start of treatment across all time points until disease progression or the end of 6 cycles of neoadjuvant therapies, whichever comes first. Response was determined by the IBCSG Head of Medical Affairs. An internal review (IR) form was created to record the final determination on best overall response. Confirmation of partial or complete response by an additional scan was not required in this trial.

Best overall response was assessed based on changes in tumor size from baseline to the assessments after 3 and after 6 cycles (denoted as day 1 of cycle 4 and prior to surgery respectively) as measured physically by caliper or ruler and as measured by breast tumor imaging (i.e., bilateral mammography and breast ultrasound).

- Complete Response (CR): The disappearance of all known disease;
 - Partial Response (PR): A 50% or more decrease in total tumor size (i.e. the product of the lesion's maximal diameter (MD) and the corresponding largest perpendicular diameter (LPD) of lesion) which have been measured to determine the effect of the therapy. In addition, there can be no appearance of new lesions or progression of any lesion;
 - Stable Disease (SD): Neither a 50% decrease in total tumor size (i.e. the product of the lesion's two diameters, MD*LPD of lesion) nor a 25% increase in the size of one or more measurable lesions has been determined;
 - Progressive Disease (PD): An increase of at least 25% in total tumor size relative to the smallest size measured during the trial and/or appearance of one or more new lesions.
6. Safety and tolerability: Adverse events (AE) were collected using CTCAE v4.0.
 - a. Each targeted AE will be classified according to the maximum grade of the event while on trial treatment (grade 0,1,2,3,4,5; where 0=no report).
 - b. Other grade 3-5 AEs will be classified according to the maximum grade of any reported other AE.
 7. Patient-reported symptoms (PRS) outcomes (see Section 2.2.6)

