15.2. Secondary objectives

Secondary objectives include evaluation with respect to several secondary endpoints as defined in section 4.2. Analyses of the secondary endpoints will be descriptive. Tests of significance, whenever applicable, will not be controlled for multiple comparisons. Due to the limited sample size, the tests will largely be underpowered except in cases where differences between treatment groups are substantial. Randomized patients who received at least one dose of study treatment are included in the analysis unless otherwise indicated.

15.2.1. Tolerability (Safety of combined neoadjuvant therapy):

Tolerability will be evaluated in each treatment arm separately. Randomized patients who received at least one dose of the trial treatment will be included in the tolerability analyses.

The frequencies of adverse events (AE) according to CTCAE 4 by type and worst grade experienced while on the neoadjuvant treatments will be summarized and tabulated by treatment arms. Two-sided 90% confidence interval (CI) for the difference in proportion of patients with each type of grade 3 or higher targeted adverse event (see section 13.2) between the treatment arms will be assessed.

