15.2.3. The Preoperative Endocrine Prognostic Index (PEPI) score at the time of surgery

Patients with available central pathology review results will be included in the assessment. See section 3.2 for the calculation of the PEPI score.

Descriptive statistics will be used to summarize the PEPI score by treatment arm. Two-sided 90% CI for the difference in the PEPI scores between the two arms will also be assessed.

For example, a patient with pathologically node-negative T1 or T2 disease, Ki67 level $\leq 2.7\%$ (or $\leq 1\%$ on a natural log scale) and persistent ER expression after completion of neoadjuvant therapy is assigned a PEPI score of 0 (best prognostic group). Logistic regression modeling will be used to explore whether the PEPI score of 0 differs from PEPI score >0 with respect to disease characteristics at baseline.

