15.2.5. Node negative disease at surgery

The percentage of patients with node-negative disease at surgery will be descriptively summarized by treatment arm. Two sided 90% CI for the difference in percentage of patients with node-negative disease between treatment arms will be assessed.

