17.1. Pathology and pathology material banking

The work of the pathologist is basic to the success of all studies. Each Participating Center should identify a pathologist responsible for study patients. The pathologist determines the diagnosis, classification, and grading of the primary tumor and evaluates the non-tumor breast tissue and local or regional spread as found in the diagnostic biopsy and definitive surgery specimen, including precise documentation of tumor size, margins of the primary, the total number of lymph nodes examined, and the number of nodes involved. All lymph nodes must be examined from each patient. If the patient has received a sentinel node biopsy, each sentinel node must be evaluated. The central review pathologist will review the submitted specimens and complete the central pathology review.

NOTE: Central pathology review on the primary tumor is mandatory for this trial, but patients will be evaluated for eligibility by tumor characteristics as determined by the local pathologist.

Both the breast diagnostic biopsy specimen and a final breast surgery specimen have to be submitted for Central Pathology Review.

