2.2.6 Analyses of secondary endpoints

- Node negative disease at surgery: The percentage of patients with node-negative disease at surgery will be descriptively summarized by treatment arm. Two sided 90% CI for the difference in percentage of patients with node-negative disease between treatment arms will be reported.
- Breast-conserving surgery (BCS):
 - Details of the surgical procedure performed overall and according to treatment arms.
 - The percent of patients in each treatment arm who had a breast-conserving surgery were presented, and the difference between the treatment arms were assessed using a two-sided exact 90% CI.
 - Rate of conversion (patient identified as candidates/planned for BCS or mastectomy per data on RA-form vs surgery performed on C-form): Cross-tabulation of surgery status between “planned” vs ‘performed’ and the percent in conversion overall and according to treatment arms were presented.
- Change in Ki67 (Surgery population, unless otherwise noted)
 - Ki67 expressions at baseline (pre-treatment, based on ITT population) and at surgery were descriptively summarized (median, IQR and mean) according to treatment arms.
 - The change in Ki67 expression from baseline (pre-treatment) to surgery was summarized for each treatment arm and two-sided 90% CI for the change were calculated and explored using a paired sample Wilcoxon signed-rank test.

- The percentage changes in Ki67 expression between the treatment arms from baseline to surgery were assessed using a two-sided 90% CI and explored using a two-sample Wilcoxon rank sum test.
- Boxplots were used to illustrate the marker distribution at baseline and surgery timepoints.
- Spider plots were used to show the individual paired Ki67 data from baseline to surgery.
- The preoperative endocrine prognostic index (PEPI) score at time of surgery
Patients in surgery population will be included in the assessment. Descriptive statistics are used to summarize the PEPI score by treatment arm. Two-sided 90% CI for the difference in the PEPI scores between the two arms maybe constructed. (*NOT DONE, given only one pt had PEPI score of 0*)
- Objective response was defined as CR/PR vs. Others (SD/PD/NE), where NE stands for non-evaluable:
 - Best overall response, overall and by treatment arm, were provided with Ns and proportions.

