3.7 POST-TREATMENT SURGERY & PATHOLOGY

Centrally pathology assessment based on surgical specimens included histology type, tumor size, Ki67 level, ER status, ER Allred score, PgR status, PgR Allred score, Her2 status as measured by IHC or FISH, vessel invasion, LN status, and PEPI score (defined as in section 2.3.2)

Table of CPR pathological characteristics, overall and according to treatment assignments.

- Ki67 and ER Allred score data: baseline, post neoadjuvant/surgery data and percent change from baseline will be summarized, difference with 90%CI
- Node negative disease at surgery: percent of patients with node-negative disease is summarized overall, by treatment arms, difference between arms using exact binominal 90% CI

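### SAP 2.2.4 defines node-negative disease by a formula that is met only when no examined node is negative, so no truly node-negative patient with a node examined can satisfy it

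*SAP*

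**What the plan says.** Node-negative disease at surgery is a listed secondary endpoint in both documents. The protocol names it in section 4.2 and plans its analysis in section 15.2.5 ("The percentage of patients with node-negative disease at surgery will be descriptively summarized by treatment arm"), but gives no rule for deriving it from node counts.

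The only counting rule is in SAP section 2.2.4, item 1: "The number of lymph nodes assessed at surgery minus the number of positive nodes identified, equal to zero".

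The SAP then uses the endpoint twice without restating the rule. Section 2.2.6 says "Two sided 90% CI for the difference in percentage of patients with node-negative disease between treatment arms will be reported". Section 3.7 plans "percent of patients with node-negative disease is summarized overall, by treatment arms, difference between arms using exact binominal 90% CI".

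Protocol section 17.1 requires the pathologist to document "the total number of lymph nodes examined, and the number of nodes involved", so both counts are recorded.

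**The concern.** The subtraction gives the number of negative nodes. Setting it to zero describes a patient without a single negative node, which is the opposite of what the endpoint's name means. Elsewhere the documents use the term in its ordinary sense. Protocol section 15.2.3 places "a patient with pathologically node-negative T1 or T2 disease" in the best prognostic group, given low Ki67 and persistent ER expression, and the PEPI table in SAP section 2.2.4 gives negative nodal status 0 points and positive status 3.

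The definition is what the derivation is programmed and validated against. Code that follows the text produces a wrong rate, a wrong difference between arms and a wrong interval. Code that is clinically right departs from the plan with nothing in the plan to justify it.

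**Working it through.** The plan states no figure to reproduce here; the check is of the logic of the rule.

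**Inputs.** Let *a* be the number of nodes assessed and *p* the number positive, with 0 ≤ *p* ≤ *a*. The SAP rule is *a* − *p* = 0 (SAP 2.2.4, item 1). The ordinary meaning is *p* = 0 with *a* ≥ 1.

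**Identity.** If *p* = 0 and *a* ≥ 1, then *a* − *p* = *a* ≥ 1, which is never zero. This needs no assumption.

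**Cases.**

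| Assessed | Positive | *a* − *p* | SAP rule | Truth | Rule correct? |
|---|---|---|---|---|---|
| 2 | 0 | 2 | not negative | negative | no |
| 15 | 0 | 15 | not negative | negative | no |
| 3 | 1 | 2 | not negative | positive | yes |
| 3 | 3 | 0 | negative | positive | no |
| 1 | 1 | 0 | negative | positive | no |
| 0 | 0 | 0 | negative | not evaluable | no |

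The 1/1 row is a lone positive sentinel node; Protocol section 17.1 provides for sentinel node biopsy. Only patients with a mix of positive and negative nodes are classed correctly.

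**Enumeration.** For *a* from 0 to 40 there are 861 pairs (41 × 42 / 2). The SAP rule selects 41: the pair 0/0 and the 40 pairs in which every node is positive. There are 40 truly node-negative pairs, and the rule selects none of them. The rule *p* = 0 with *a* ≥ 1 selects all 40 and no node-positive pair.

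**Size under assumed shares.** The documents give no nodal distribution. Let *t* be the share truly negative and *q* the share with all nodes positive, and suppose every patient has at least one node examined. The literal rule then reports *q* in place of *t*, and misclassifies *t* + *q*.

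| Assumed *t* | Assumed *q* | Reported rate | True rate | Misclassified |
|---|---|---|---|---|
| 0.30 | 0.00 | 0% | 30% | 0.30 + 0.00 = 30% |
| 0.50 | 0.10 | 10% | 50% | 0.50 + 0.10 = 60% |
| 0.70 | 0.20 | 20% | 70% | 0.70 + 0.20 = 90% |

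Any patients with no node examined would add their share to the reported rate and to the misclassified share.

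**The arm difference can change sign.** Assumed example, 25 per arm: 12 truly negative in arm A and 10 in arm B; 1 with all nodes positive in A and 3 in B. Intervals are Newcombe hybrid score at 90%, built from the Wilson limits (*l*, *u*) of each proportion: lower = *d* − √[(*p*B − *l*B)² + (*u*A − *p*A)²], upper = *d* + √[(*u*B − *p*B)² + (*p*A − *l*A)²].

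- True: B 10/25 = 0.40 (0.256 to 0.563), A 12/25 = 0.48 (0.326 to 0.638). Difference −0.08, 90% CI −0.294 to +0.144, width 0.438.
- Literal rule: B 3/25 = 0.12 (0.049 to 0.265), A 1/25 = 0.04 (0.009 to 0.161). Difference +0.08, 90% CI −0.060 to +0.229, width 0.289.

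SAP 3.7 names an exact interval for this difference. One exact unconditional version (score statistic inverted) gives about −0.31 to +0.16 and −0.06 to +0.25. The sign change is the same; both intervals are a little wider.

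**The case against.** The intended meaning is plain from the endpoint's name, the PEPI table and Protocol 15.2.3, so a programmer would probably have read through the slip. SAP 3.7 also lists "vessel invasion, LN status, and PEPI score" among the central pathology items and reports the node-negative percentage in the same section, so the rate may have been taken from a recorded nodal status and the formula never used. The endpoint carries little inferential weight: Protocol 15.2 says "Analyses of the secondary endpoints will be descriptive". The SAP already notes some analyses as not performed in light of the data, so rewriting the text now cannot restore pre-specification.

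Much of this stands. The documents do not show that the formula was applied, the two-arm example shows what is possible rather than likely, and checking the program matters at least as much as changing the words. It does not remove the defect. The formula is the only counting rule in either document, and neither later SAP section corrects it or says that recorded nodal status is used instead. Reading it charitably as zero positive nodes still leaves a patient with no node assessed counted as node-negative. Protocol 17.1 expects all nodes to be examined, so that group may be small or empty, but neither document says how she is classed.

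**Conclusion.** The definition is wrong as written. This rests on an identity, not on any assumption about the data. Followed literally, it excludes every truly node-negative patient with a node examined and admits patients whose examined nodes are all positive, or who had none examined.

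The actual effect on results is unknown. The misclassified share of 30–90% and the reversed arm difference rest on assumed distributions. The primary endpoint and the sample size are untouched. PEPI takes nodal status from central pathology review and does not cite this formula. The correction is needed because the stated rule for a listed endpoint reverses its meaning, not because an erroneous result has been shown.

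**What to change.** - **Replace the definition** in SAP 2.2.4, item 1, with: node-negative disease at surgery means that the number of positive nodes is 0, with at least one lymph node assessed at surgery.
- **State how patients with no node assessed are handled.** Report them separately as not evaluable and say whether they are in the denominator. One workable convention takes the surgery population with at least one node assessed as the denominator. A sensitivity rate over the whole surgery population, counting them as not node-negative, is optional.
- **Check the derivation program** and any rate already reported against the corrected rule, and record whether the counts or the central pathology nodal status were used. In the same check, confirm that the PEPI nodal item does not draw on the formula.
- **Date the correction** and describe it as a clarification made after the analyses the SAP reports.

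The cost is one line of text, one sentence on the denominator and a program check. Both counts are already documented under Protocol 17.1, so no new data are needed.
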